#### o Tropicamide 0.8% /Phenylephrine 5%

#### 6.4 Procedure to monitor and measure adherence

For more than four decades, numerous investigations have been conducted on the appropriate way to measure and quantify adherence to medications, however none has reached a consensus to establish itself as the gold standard, both in cross-sectional and longitudinal studies. [31, 32, 33, 34, 35, 36, 37, 38]

There are different procedures to measure adherence to pharmacological interventions. The most common procedure involves self-reports, these include: patient interviews, questionnaires and self-monitoring diaries. Its strengths are speed, flexibility, low cost and ease of implementation; they have a high degree of specificity for non-adherence, however, the sensitivity and reliability for adherence is low. [38, 39]

Biochemical measurement of the drug, or its metabolite, is one of the methods that best confirms the use of the drug. However, in addition to being costly and impractical, it is of little use in the context of ophthalmic applications, as concentrations at the peripheral level could be undetectable; and samples from other tissues involve more invasive methods that would not be advisable. [38] Counting medication is another way to measure adherence. Classically referred to as "pill count", in ophthalmology it translates to the weight of the bottle. This is a simple, inexpensive, and non-invasive method. The main disadvantages of this method are: 1. The application of the drug cannot be confirmed (it may have been intentionally thrown or instilled out of the eye) and 2. Depends on the subject bringing the medication back. [38, 39]

The approach with multiple adherence measurement procedures is recommended. Because there is no ideal adherence measurement, it is appropriate to use more than one method when trying to achieve realistic results. Selecting two or more methods allows their strengths and weaknesses to be offset, to more accurately capture adherence levels. [37]

Due to the characteristics of the containers, the evaluation of adherence will be favored through the subject's diary. The following simplified formula will be used:

$$Ad = (A_r)100/A_i$$

Ad = Adhesion

Ar = Registered applications

Ai = Applications indicated for the products under investigation

There is no standardized parameter to define adequate adherence, it must be defined and delineated by the objectives of the particular research. [38]

For this study, it will be considered that a minimum adherence of 70% is what is necessary to meet the research objectives. Therefore, subjects who present an adherence of less than 70% will not be considered for the efficacy analysis, they will only enter the safety analysis.

Study No: SOPH037-0119/I Version 1.0 31-January - 2019

### 6.5 Strategies to improve adherence

- 1. The IP will sensitize the subject on the importance, to achieve the objectives of the study, of the correct application of the IP.
- 2. Direct questioning by the IP about the application of the IP.
- 3. Delivery of a printed calendar specifying the date of the visit and its activities.
- 4. Training in filling out and reviewing the "Subject's Diary".
- 5. If deemed necessary, text messages may be sent as reminders. The content of these messages must be previously approved by the CEI.

# 7. Study methods and procedures

#### 7.1 From the research center

The present study will be carried out in a research center previously evaluated by the sponsor. This center will be an institution or establishment where health research is carried out that complies with current regulations.

The research center will be responsible for forming a multidisciplinary research team to execute the clinical study according to protocol. It is their prerogative to design the organization and select the personnel who will carry out the functions. However, it is the sponsor's need for the Principal Investigator (PI) to be an ophthalmology specialist.

Any person who is appointed, under their responsibility, a part of the study follow-up (co-investigator, sub-investigator, nurse, etc.) or a specific role for participation in the study (pharmacist, administrative assistant, study coordinator, etc.) It must appear in the "Delegation of Responsibilities".

The competence and training of any person who has direct participation in the study activities must be verified before carrying out any activity related to the protocol. The foregoing must be recorded and the documents that constitute evidence of this competence and / or training must be kept in the master file of the study. The competence and training of the personnel who have functions in the study, both at the central level and in the study centers is the responsibility of the sponsor.

The sponsor must ensure that all the personnel of the study centers participating in the study are adequately trained on the study (research protocol, investigator's manual, amendments, standard operating procedures, etc.) and on the Good Clinical Practices of the ICH, before the start of your participation in it. Training must be recorded in writing and those records must be filed in the study master file.

#### Clinical study registration

This clinical study will be registered by the sponsor in public registries of clinical trials before its initiation (inclusion of the first patient): National Registry of Clinical Trials (RNEC) of the Federal Commission for the Protection against Sanitary Risks (COFEPRIS) and on a platform WHO primary registry. WHO Primary Registries meet specific criteria for content, quality and validity, accessibility, unique identification, technical capacity, and administration. WHO Primary Registries meet the requirements of the International Committee of Medical Journal Editors (ICMJE).

### 7.2 Randomization and Blinding

Subject randomization will be carried out using a computerized assignment system. After signing the FCI, the patient will receive a patient number with which all their information will be coded pseudo anonymously during collection and completely anonymized during analysis.

The generation will be carried out by a third party, authorized by Sophia Laboratories S.A. of C.V., through its electronic system. The information for this third party will be in the file.

Although it is an open study, the secondary container will be masked.

PIs will be identified by means of labels in accordance with current and applicable regulations, they must contain at least:

- Name, address and telephone number of the sponsor.
- Pharmaceutical form and route of administration.
- Lot Number.
- Legend "Exclusively for clinical studies"
- Date of Expiry.

#### 7.3 Outcomes Variables

#### 7.3.1 Primary outcome Variables

- Incidence of adverse events (AE) (Evaluation Time: day 8 and 10).
- Score of the Ocular Comfort Index (ICO) (TE: day 8).

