#### Statistical methodology:

The data will be expressed with measures of central tendency: mean and standard deviation for the quantitative variables. The qualitative variables will be presented in frequencies and percentages. The statistical analysis will be carried out by means of the Mann-Whitney U test for the quantitative variables for the difference between the groups. The difference between the qualitative variables will be analyzed using X2 (Chi2) or Fisher's exact. An  $\alpha \le 0.05$  will be considered significant.

Version 1.0 31-January - 2019

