#### 7.3.3.2 ICO score

The ICO is a questionnaire designed to measure the irritation of the ocular surface with Rasch analysis to produce estimates on a linear interval scale (scores: 0-100). Similar to the index for ocular surface diseases, the ocular comfort index (ICO) assesses symptoms. The ICO contains items that focus on discomfort associated with ocular surface disturbances. Each of these questions has two parts, which separately inquire about the frequency and severity of symptoms. [40]

The evaluator will deliver the questionnaire to the subject and will allow him to answer it calmly without any pressure and / or coercion, he will only assist him if he has difficulty understanding any of the questions.

Management as AE: The ICO assesses symptoms, which may or may not be related to an AE. The score obtained from the ICO alone should not be considered an EA.

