#### Handling as EA: your presence will be considered as an EA.

#### 7.4 Program of visits and study activities

#### 7.4.1 Description of activities per visit

The procedures are listed in the order that they are suggested to be performed, trying to maintain the coherence of the evaluations and, as far as possible, from the least invasive to the most invasive.

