#### 7.4.1.1 Basal visit

- -FCI Signature: refers to the signature of the written informed consent document. Without obtaining informed consent, it is not possible to perform any of the study procedures
- -Clinical history: refers to the technical, clinical and legal document in which the subject's health conditions, medical acts and other procedures performed on the subject are chronologically recorded. It includes anthropometric measurements, anamnesis, comprehensive ophthalmological examination that allows discerning the eligibility of the patient, that is, evaluation of both eyes of ocular attachments, slit lamp examination of the ocular surface and anterior segment, and funduscopy. If the subject is taken from the established population base of the study center, the existing clinical history may be used, only an update being required.
- -Evaluation of concomitant medications: refers to the questioning by the PI of the subject, inquiring about the use of medications.
- Pregnancy test in urine: It refers to the realization of a rapid pregnancy test in all women of childbearing age who wish to enter the study. By childbearing age we understand women who have had their menarche and have not had their menopause. Menopause is defined as 12 months from the last menstruation in women over 40 years of age, or who have undergone a bilateral hysterectomy or oophorectomy. Women of childbearing potential with contraceptive methods including bilateral tubal obstruction should undergo a pregnancy test. This test will be performed by the IP or the designated team person in accordance with the instructions of the device provided by the sponsor
- -Vital signs: refers to the taking of heart rate, respiratory rate, systemic blood pressure and temperature. This information must be contained in the patient's medical record and the progress notes of the patient's clinical record.
- -MAVC: See 7.4.3.2
- -ICO: See 7.4.3.2
- Ocular surface stains: See 7.4.3.4 and 7.4.3.5
- Ophthalmological evaluation: See 7.4.3.1
- -Eligibility criteria: refers to the review by the PI, where it verifies that the subject can be included in the study by meeting the inclusion criteria and not meeting the exclusion criteria. See 5.1

- -Assignment of PI: It refers to determining the intervention that the patient will follow during the study. It will be carried out according to section 7.3. This assignment will be made at the baseline visit (day 1).

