#### 10.1.2 Interpretation of data

The Kolmogorov-Smirnov tests will be carried out to know if the distribution presents normality in the results obtained in each study group. [fifty]

The results of the continuous quantitative variables will be presented in measures of central tendency: mean, standard deviation and ranges.

The statistical analysis of the continuous quantitative variables to find significant differences (p < 0.05) will be as follows:

- Intra-group analysis: they will be determined using the Wilcoxon rank test for quantitative variables. [51]
- •
- Between-group analysis: The differences between the groups will be analyzed using the Mann-Whitney U test.

The level of difference to consider significance will be an alpha ( $\alpha$ ) of 0.05 or less.

The result of the nominal and ordinal qualitative variables will be presented in frequencies, proportions and percentages.

The statistical analysis to identify significant differences of the qualitative variables will be carried out by creating 2x2 contingency tables and will be carried out as follows:

- Intragroup difference: McNemar test. [52] Which is applied to 2 × 2 contingency tables with a dichotomous trait, with pairs of matched subjects, to determine if the marginal frequencies of row and column are equal (marginal homogeneity).
- Difference between groups: Pearson's Chi-square test (X2) or Fisher's exact test in expected values less than 5.

The level of difference to consider significance will be an alpha ( $\alpha$ ) of 0.05 or less.

For the reporting of adverse events, all the eyes of those participants who were randomly assigned to an intervention group after the baseline visit will be considered. The results will be expressed in number of subjects.

The final report of the results will be shown in tables or graphs, as appropriate.

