#### 10.1.5 Subjects included in the analysis

Those subjects who comply with an adherence ≥75% will be included in the statistical analysis to fulfill the objective of the study, taken from the subject's diary.

The investigational drug will be considered safe and effective when there are no clinical and statistical differences in all the primary outcome variables, with respect to its comparator (Lagricel® Ofteno, unit dose).

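### The primary between-arm ICO comparison ignores the baseline ICO score that the trial already collects, so precision is lost in proportion to the correlation between the two scores

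*Combined protocol and SAP*

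**What the plan says.** The primary outcome in section 7.3.1 is "Score of the Ocular Comfort Index (ICO) (TE: day 8". It is worded as a score, whereas most secondary outcomes in section 7.3.2 are worded as changes. Section 2.3.2 names the ICO score as the measure for comparing tolerability.

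Baseline ICO is collected. It appears in the schedule in section 1.2, in the ICO row of Table 2 (section 7.3.3, baseline and final visits), and among the baseline procedures in section 7.4.1.1 ("ICO: See 7.4.3.2").

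The between-arm analysis is given in three places. The Synopsis says it is done "by means of the Mann-Whitney U test for the quantitative variables". Table 2 names the same test for ICO. Section 10.1.2 says "The differences between the groups will be analyzed using the Mann-Whitney U test". None includes a covariate. Baseline enters only through the within-group Wilcoxon test, which does not compare the arms. No between-arm estimate or interval is specified for ICO.

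Section 7.3.3.2 describes the instrument as designed "to produce estimates on a linear interval scale (scores: 0-100", so a difference in points is meaningful. Section 10.1.5 accepts the product "when there are no clinical and statistical differences in all the primary outcome variables".

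**The concern.** When a pre-treatment measurement of the same outcome exists, part of the spread in day-8 scores is stable variation between people. An unadjusted comparison leaves that variation in the error term. The trial pays for the baseline questionnaire but does not use it to compare the arms.

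This matters more than usual for two reasons. The sample size in section 10.2.2 was derived from adverse-event proportions, and the documents give no ICO standard deviation, target difference or margin, so nothing shows that 17 per arm is enough for ICO. And because section 10.1.5 treats the absence of a difference as success, an imprecise comparison makes acceptance easier.

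**Working it through.** **Inputs from the plan.** 17 subjects per arm (14 × 1.2 = 16.8, rounded up to 17, section 10.2.2); significance level 0.05; one questionnaire per subject, so ICO raises no two-eye issue. The plan has no ICO power figure to reproduce.

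**Assumptions.** Two-sided test (the plan does not state sidedness for ICO); latent baseline/day-8 correlation ρ of 0.3, 0.5 or 0.7; true difference 0.8 SD, with 0.5 SD as a smaller case; 0%, 50% or 80% of controls at the scale floor.

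**Analytic check, normal scores.** Adjustment multiplies the variance of the between-arm difference by 1 − ρ².
- Variance factor: 1 − 0.09 = 0.91; 1 − 0.25 = 0.75; 1 − 0.49 = 0.51.
- CI width factor (square root): 0.95; 0.87; 0.71.
- Equivalent subjects per arm: 17/0.91 = 18.7; 17/0.75 = 22.7; 17/0.51 = 33.3.
- Smallest difference detectable with 80% power, unadjusted: (1.960 + 0.842) × √(2/17) = 0.96 SD. Adjusted: 0.92; 0.83; 0.69 SD.
- At ρ = 0 nothing is gained, and estimating the slope costs about 3% in variance.

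**Simulation, 20,000 trials per setting.** Bivariate normal scores, with the floor made by censoring both visits at the control percentile. Rank ANCOVA regresses the pooled day-8 ranks on arm and pooled baseline ranks. The Monte Carlo standard error is at most √(0.25/20,000) = 0.35 points.

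| Controls at floor | True difference | Mann-Whitney | Rank ANCOVA, ρ = 0.3/0.5/0.7 |
|---|---|---|---|
| 80% | 0.8 SD | 45% | 46/48/55% |
| 50% | 0.8 SD | 56% | 58/64/75% |
| none | 0.8 SD | 59% | 62/69/83% |
| 80% | 0.5 SD | 19–20% | 20/21/23% |
| 50% | 0.5 SD | 26% | 27/30/37% |
| none | 0.5 SD | 27–28% | 29/33/45% |

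The floor weakens the observable correlation: latent 0.3/0.5/0.7 becomes 0.24/0.43/0.63 with half at the floor and 0.17/0.33/0.54 with 80%. At latent correlations of 0, 0.1 and 0.2 the two tests differ by about 1 point at most, in either direction. Type I error was 4.6–5.3% for Mann-Whitney and 4.7–5.4% for rank ANCOVA.

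With 14 evaluable per arm and 0.8 SD, the figures are 51% against 54/60/75% (no floor) and 37% against 38/40/46% (80% floor).

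**Change score.** With equal variances at the two visits, its variance factor is 2(1 − ρ) = 1.4/1.0/0.6, against 0.91/0.75/0.51 for adjustment. The gap is (1 − ρ)², which is never negative. In simulation at 0.8 SD, Mann-Whitney on change has 46/59/81% with no floor, against 62/69/83% for rank ANCOVA. At the 80% floor it has about 36/42/55%, against 46/48/55%, so there the two are nearly level at ρ = 0.7.

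**Ordinary ANCOVA.** At the 80% floor and 0.8 SD its power is 39/41/48%, below Mann-Whitney at ρ = 0.3 and 0.5. Its 95% interval covers 92–94% there, against about 95% with no floor or a 50% floor.

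**The case against.** The strongest reply is that nothing in the plan is wrong. A Mann-Whitney test on a day-8 score is a coherent choice for a 34-subject phase I study, and ICO did not drive the sample size. That stands. A reader might infer that the unadjusted test is biased or invalid, but under randomisation it is neither.

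The second reply is that the gain may be small here. Subjects are clinically healthy, aged 18 to 45 and without active ocular inflammation, so many scores near zero are plausible. The questionnaire asks about the past week, so the baseline covers a period before the lifestyle restrictions and any stop in lens wear, which could weaken the correlation. This also stands. In the 80% floor case the gain at 0.3 and 0.5 is about 1 and 3 points, and the 83% figure needs both no floor and a correlation of 0.7.

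Third, the decision would seldom change for a small effect: at 0.5 SD, rank ANCOVA still misses a true difference in about 55–80% of trials. That is correct, and it limits the weight of the point.

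Fourth, pairing a rank test with an ordinary-ANCOVA interval can produce conflicting answers. At 0.8 SD the two disagreed on significance in 7–8% of simulated trials with no floor, 12–13% at a 50% floor and 18–20% at an 80% floor. The plan must therefore say which one is the test.

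A reader might also infer from the row order in section 1.2 that baseline ICO is completed after the open-label arm is known. The documents do not support this. The schedule is a checklist, while section 7.4.1 states that "The procedures are listed in the order that they are suggested to be performed", and section 7.4.1.1 places ICO before assignment.

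**Conclusion.** The point holds as an efficiency improvement worth considering. The primary ICO comparison leaves a collected baseline unused. At 17 per arm and 0.8 SD the power forgone is about 0–10 points with a heavy floor, 2–19 with half at the floor and 3–24 with none, over assumed correlations of 0.3 to 0.7. It is essentially nil at 0.2 or below. The correlation, the floor proportion and the true difference are all assumptions, so confidence in the size is only medium. That baseline is unused between arms follows directly from the text.

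Two wider readings should be resisted. Baseline adjustment does not repair the acceptance rule in section 10.1.5: taking non-significance as evidence of similarity, with no ICO margin, is a separate problem. And the ordinal staining and hyperemia grades, for which section 10.1.2 says the analysis "will be carried out by creating 2x2 contingency tables", are secondary outcomes. Any loss there would rest on grade distributions that the documents do not give, so they are not part of this conclusion.

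**What to change.** In the Synopsis, the ICO row of Table 2 and section 10.1.2, name rank ANCOVA as the single pre-specified between-arm test for ICO: rank day-8 ICO and baseline ICO across both arms, regress the day-8 ranks on arm and baseline ranks, and test the arm term. State that the choice does not depend on the normality test or on the observed correlation.

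Also report the mean difference in ICO points adjusted for baseline, with its 95% CI from ordinary ANCOVA, as a supporting estimate only. Say in the plan that it can disagree with the rank test, and that its coverage falls to about 92–94% if most subjects are at the floor and a true difference exists. Do not substitute a raw change score.

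The cost is wording in three places, slightly more analysis work and one degree of freedom. No visit, subject or measurement is added. The downside is little or no gain, with a loss of about 1 point at worst, if the correlation is low, and only a small gain if the floor is heavy.

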#### 7.3.2 Secundary outcome variables

- -Changes in the BCVA (TE: day 8).
- -Changes in corneal and conjunctival staining with lysamine green (TE: 8).
- -Changes in corneal and conjunctival staining with fluorescein (TE: day 8).
- -Conjunctival hyperemia changes (TE: day 8).
- -Incidence of chemosis (TE: day 8)

#### 7.3.3 Definition of variables, methods and scales to be used for their measurement

Variable	Туре	Unit (Symbol)	Method of measurement	normal value	evaluation time	statistical test
Primary						
Adverse events	Discreet	Number of cases (n)	Counting	0	VB, V1, VF y LLS	U de Mann- Whitney
events	Categoric al nominal	Present/ absent	Observation	Absent	LLS	χ2 or exact by Fisher
Score of	Discreet	Points	Questionnaire	NA	VB, VF	U de Mann- Whitney
Secondary						
MAVC	Discreet	Fraction	Poster of Snellen	1	VB, V1 y VF	U de Mann- Whitney
Corneal and conjunctival fluorescein staining	Ordinal	Levels	Direct observation with slit lamp and cobalt blue filter, Oxford scale graduation	0	VB, V1 y VF	χ2 or exact by Fisher
Corneal and conjunctival staining with lysamine green	Ordinal	Levels	Direct observation with slit lamp, Oxford scale graduation	0	VB, V1 y VF	χ2 or exact by Fisher
Conjunctiv al hyperemia	Ordinal	Normal / Very Mild / Mild / Moderate / Severe	Direct observation. Clasification of Efron.	Normal	VB, V1 y VF	χ2 or exact by Fisher
Chemosis	Categorical nominal	Present / absent		Absent	VB, V1 y VF	χ2 or exact by Fisher

Table 2. Defoperational definition of variables

The variables, the method and scales for their measurement are described in detail below. They are in order according to Table 2

